## 8.2. Methods Used to Assess, Record, and Analyze the Efficacy Parameters

From the beginning of the trial, the subjects shall attend five scheduled visits (baseline visit, three follow-up visits, and the end of trial visit) with the study physician and unscheduled visits whenever their clinical condition warrants it.

During the baseline visit, the study doctor will conduct a detailed clinical interview during which the following will be recorded and performed:

- Screening of patients meeting the inclusion criteria.
- Signing of the informed consent form by the patient and the investigator.
- Collection of demographic data and ensuring that the patient will reside in the Autonomous Community of Madrid throughout the study period (September to May).
- Measurement and recording of vital signs (BP and HR).
- Collection of tobacco consumption data using the following formula: no. of cigarettes/day x no. of years/20 (baseline visit and visits 1, 2, 3, and 4).

- Testing for exhaled CO measure (all visits).
- Detailed medical history and general examination of the patient will be conducted, recording the data in the CRF (baseline visit and visits 1, 2, 3, and 4).
- Female subjects included in the study must provide a urine sample (first morning void) on which a pregnancy test will be performed based on a qualitative one-step chromatographic immunoassay (Acon) determining the presence of beta-human chorionic gonadotropin (beta-HCG). Subjects with a positive pregnancy test will not be included in the trial.
- Collection of blood from each subject (baseline visit, month 6, month 12, and end of trial visit at month 18) and analysis of the following parameters:
  - Complete blood count (flow cytometry).
  - Blood biochemistry, including basal blood glucose levels and liver function tests (enzymatic methods).
  - Viral serology testing: HCV, HBV, and HIV (ELISA serology).
  - General immunological parameters.
- All patients included in this trial will undergo a spirometry test during the baseline and end of trial visits (visits 4, at 12, 15, and 18 months from the start of the vaccination). Spirometry testing will be performed using the spirometer according to the protocol of the Respiratory Function Tests Unit of all hospitals participating in the trial.

[name]  
Traductor-Intérprete Jurado de INGLÉS  
Nº 9971

- Any concomitant medication will be recorded in the CRF during all visits.

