6.1.3. Safety outcomes

- ★ Overall rate, severity, and relationship of any adverse event per administration and patient.
- ★ Assessment of local tolerability (tissular reactions in the administration site).
- ★ Changes in standard laboratory parameters (serum chemistry and hematology).

7. Statistical Methods

All statistical analyses will be carried out by Inmunotek.

All computation will be performed according to European Guidelines

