7.1. General Considerations

Descriptive statistics will be provided for selected demographic, safety, and exacerbations by dose, dose schedule, and time as appropriate. Descriptive statistics on continuous data will include means, medians, standard deviations (and standard errors for post-baseline data), quartiles, and ranges, while categorical data will be summarized using frequency counts and percentages. Graphical summaries of the data may also be presented.

When data are summarized by time, the values recorded against the scheduled time points listed in the protocol will be used. When assessing minimum/maximum increases or decreases over the study, all assessments, including unscheduled assessments will be used. Data listings will include all available data from all enrolled subjects unless specified otherwise.

This analysis does not use significance levels. Exact, two-sided 95% confidence intervals were used for the Histamine equivalent concentration.

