7.5. Safety Evaluation

All adverse events of the trial will be coded according to MedDra classification. MedDra version will be communicated in the statistical report. The safety variables will be compared using the chi-square test in the case of qualitative variables or Student's T test in the case of quantitative variables whenever they meet parametric assumptions, or using non-parametric test in the opposite case. AEs will be summarised by System Organ Class and Preferred Term displaying number of subjects, number and percentage of subjects having the event as well as number of events. Furthermore, the AEs will be summarised according to severity, relationship, outcome and seriousness.

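### Numeric laboratory changes are compared between arms only on location; no abnormality criterion, shift table or by-arm count of affected subjects is defined

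*SAP*

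**What the plan says.** SAP 6.1.3 lists as a safety outcome "Changes in standard laboratory parameters (serum chemistry and hematology"). Protocol 5.1 and 8.1 list the same outcome. Protocol 8.2 shows what is collected: a full blood count and biochemistry that includes glucose and liver function tests, at baseline and months 6, 12 and 18.

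SAP 7.5 gives the comparison in one sentence. It opens with "The safety variables will be compared using the chi-square test in the case of qualitative variables" and continues, for quantitative ones, with Student's "T test in the case of quantitative variables whenever they meet parametric assumptions, or using non-parametric test in the opposite case". The non-parametric test is not named. Protocol 10.1 has the same rule.

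Counts of subjects appear in SAP 7.5 for adverse events only, "displaying number of subjects, number and percentage of subjects having the event as well as number of events".

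Three items in SAP 7.1 could bear on laboratory data:
- "Descriptive statistics will be provided for selected demographic, safety, and exacerbations by dose, dose schedule, and time as appropriate"; for continuous data these include quartiles and ranges.
- "When assessing minimum/maximum increases or decreases over the study, all assessments, including unscheduled assessments will be used".
- Listings of all available data for all enrolled subjects.

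**The concern.** A laboratory change is numeric, so it falls under the quantitative rule. A t test compares means. The usual non-parametric tests compare ranks or medians. All of them answer whether one arm's values as a whole sit higher or lower than the other's. Harm from a product often looks different: most subjects are unchanged and a few have a large rise, for example in a liver enzyme. The clinical question is then how many subjects per arm crossed a limit, and whether they were already beyond it at baseline. No planned table answers that.

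SAP 2.2 puts safety in the scope of the clinical study report. A cluster of marked abnormalities on active treatment could therefore be summarised by a non-significant comparison of means or medians, with no table beside it to show the imbalance.

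**Working it through.** The documents give no figure for laboratory safety, so there is no plan figure to reproduce. The check has two parts: what the plan would show, and how sensitive the planned tests are.

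**1. What each planned output shows for laboratory data**

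| Planned output | Counts affected subjects by arm? | Relates them to baseline? |
|---|---|---|
| t or non-parametric test of change (SAP 7.5) | No | Only through the mean or median change |
| Chi-square for qualitative safety variables (SAP 7.5) | It could, but no laboratory category is defined | No |
| Ranges, minimum/maximum change (SAP 7.1) | No; an extreme is one value per arm | No |
| Listings (SAP 7.1) | No; not flagged or tabulated | Only by reading each subject's rows |
| Adverse event tables (SAP 7.5) | Only if the value was reported as an event; no rule says when | No |

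**2. Assumptions for the sensitivity check**

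Group size: SAP 7.1.1 plans 90 per group with 20-25% dropout, so 90 × 0.80 = 72 to 90 × 0.75 = 67.5; I use 70. Analyte (assumed): log-normal, mean 25, SD 10. Affected subjects (assumed): k on active with values near 200 (SD 20), none on placebo. Tests are two-sided at 0.05 (sidedness is not stated in the documents).

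**3. Mann-Whitney by hand**

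Putting k of n active subjects at the top of the ranks changes the chance that an active value exceeds a placebo value from 0.5 to 0.5 + 0.5k/n. The null standard error is √[(2n+1)/(12n²)] = √[141/58,800] = 0.0490.

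- k = 5: shift 0.5 × 5/70 = 0.0357; z = 0.0357/0.0490 = 0.73; power ≈ Φ(0.73 − 1.96) + Φ(−0.73 − 1.96) = 0.109 + 0.004 = 0.113.
- k = 3: shift 0.0214; z = 0.44; power ≈ 0.064 + 0.008 = 0.072.

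The size of the abnormal values does not enter: 200 and 2,000 give the same answer.

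**4. Simulation, 70 per arm (chance of p<0.05)**

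| Affected (active v placebo) | t test | Mann-Whitney | Mood's median, continuity-corrected |
|---|---|---|---|
| 3 v 0 | 17-18% | 6-7% | 3% |
| 5 v 0 | 75-79% | 10-11% | 4% |

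Ranges are across repeat runs. Without the continuity correction Mood's test gives about 8.5% at 5 v 0.

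A second set-up, with normally distributed values, affected subjects shifted by 5 to 10 SD and 90 per arm, points the same way. At 6 v 0: t test 35-67%, Mann-Whitney 11%, Mood 6-8%, and Fisher's test on the count of subjects above 3 SD 78-89%.

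**5. What a count would show**

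For k v 0 with n per arm, the two-sided Fisher p = 2 × C(n,k)/C(2n,k).

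- 3 v 0: 2 × (70·69·68)/(140·139·138) = 0.24; risk difference 3/70 = 4.3 points.
- 5 v 0: 2 × (70·69·68·67·66)/(140·139·138·137·136) = 0.058; risk difference 5/70 = 7.1 points.

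The chi-square named in SAP 7.5 is not safe here. At 5 v 0 the expected count per arm is 5 × 70/140 = 2.5, and the uncorrected statistic is 140 × (5 × 70)²/(70 × 70 × 5 × 135) = 5.19, p = 0.023, against the exact 0.058.

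**6. Do the abnormal values cause the switch of test?**

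With the log-normal analyte and no affected subject at all, Shapiro-Wilk at 0.05 already rejects normality in at least one arm in about 99% of trials. With near-normal values, 70 per arm, rejection is about 9% with none affected and about 96% with one subject shifted by 6 SD.

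**The case against.** The strongest case against is that the plan is fuller than the t-test clause suggests. The same sentence provides a chi-square for qualitative safety variables. SAP 7.1 plans ranges, a rule for maximum changes and complete listings, so every abnormal value will be on paper. An abnormality reported as an adverse event is counted by preferred term, severity and relationship.

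All of that is true, and it narrows the point without removing it. No laboratory category exists to feed the chi-square. The SAP 7.1 descriptives cover selected safety data, and a maximum cannot tell one affected subject from six. A listing is not a comparison. No rule says when a laboratory value becomes an adverse event.

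A second objection is that with 3 to 5 affected subjects a significance test on the count also fails (Fisher p = 0.24 and 0.058). That stands. In this range the loss is the missing table more than the choice of test.

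A reader might infer more than the documents support:
- That a few abnormal values trigger a switch to a weaker test. This can happen with near-normal change scores. For a skewed analyte the non-parametric test is the default whether or not harm occurs.
- That the plan prescribes a rank test. SAP 7.5 names none; Mann-Whitney and Mood's test are named in SAP 7.4 for efficacy, and I use them as examples.
- That an imbalance would be reported as no difference. With ranges and listings planned, it could be; it need not be.

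**Conclusion.** The point holds in this form. Numeric laboratory changes, a stated safety outcome, are compared only on location, and nothing in either document counts subjects with a marked abnormality by arm or relates them to baseline. In the assumed example of 5 affected against none with 70 per arm, the non-parametric route reaches p<0.05 in about 10% (Mann-Whitney) or 4% (Mood, continuity-corrected) of trials, little different from the 5% chance level. The t test does better at 5 v 0 but reaches only 17-18% at 3 v 0.

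The percentages rest on assumed values for the analyte, the number affected and the size of the abnormality. The hand calculation for Mann-Whitney needs only the number affected and the group size. The absence of a count rests on the text alone. This is a worthwhile and cheap improvement to the safety analysis; it does not touch efficacy.

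**What to change.** In SAP 7.5, for each chemistry and haematology parameter, add:

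- (a) A by-arm shift table from baseline to worst post-dose value (below, within or above the laboratory reference range). Say whether unscheduled values count, and whether month 18, six months after treatment ends, is included or shown separately.
- (b) The number and percentage of subjects per arm with a marked abnormality, defined by multiples of the reference limit fixed before unblinding, with the risk difference and an exact 95% confidence interval.
- (c) A flag for those subjects in the listings already planned.

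Keep the mean or median change as a descriptive summary.

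Cost: limited extra programming on data already scheduled at baseline and months 6, 12 and 18, with no added visits or samples. The limitation to state in the report is that a count of 3 to 5 against none is informative but not significant at the 0.05 level.

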### **Duration of the Trial**

The trial is scheduled to comprise a 12-month treatment period and a 6-month post-immunization follow-up period (18 months total per subject). The trial shall end with the trial's database lock.

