**All subjects will start treatment with Bactek vs. placebo in a stable clinical condition.**

- The subjects shall attend study visits every 3 months and whenever they develop symptoms of respiratory infection.
- They must strictly record the number of days of oral or systemic antibiotic treatment required until the remission of their ailment (COPD exacerbation).
- The number of days of hospitalization required due to the severity of the clinical condition (COPD exacerbation both during and after the immunization [6 months]) will be strictly recorded until the patient's clinical symptoms resolve and they are discharged home in a stable clinical condition.
- The pre- and post-immunization quality of life will be recorded using the specific CAT survey.
- Baseline Visit (prior to the start of the treatment)

The baseline visit can take place 1-4 weeks before the start of the treatment (visit 1), and the following tests will be performed that day (Table 1):

- Informed consent.

- Inclusion and exclusion criteria.
- Demographic data (including residence data).
- Vital signs (body temperature [BT] and HR).
- Tobacco consumption (no. of cigarettes/day x no. of years/20).
- Medical history/complete examination (description of the abnormality).
- Measured exhaled CO.
- Collection of blood samples to perform the following tests:
  - ~ Hematology
  - ~ Serum chemistry
  - ~ Viral serology testing
  - ~ Immunological assessment

A blood sample of each patient will be collected during the baseline visit for the following:

- Determination of serum levels of IgG, IgA, and IgM. In patients with IgG levels <500 mg/dl or IgA levels <6 mg/dl, a determination of the IgG subclasses will be performed (nephelometry, Beckmann Coulter, USA) to rule out an immunodeficiency.
- Serum concentration of the anti-pneumococcal and anti-tetanus toxoid antibodies. An *in vivo* response study will also be performed in patients with low levels of antibodies in order to rule out an immunodeficiency in antibody

production.

- Spirometry.
- Recording of concomitant medication.
- Pregnancy test (for women of childbearing age).
- Recording of the consumption of healthcare resources.
- Subject's visual analog scale score.
- Investigator's visual analog scale score.
- Quality-of-life questionnaire.
- Comments.
- CRF review.

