#### 7.1.4. Treatment Periods, Including the Follow-up Period

The treatment and follow-up periods will jointly last 18 months (12 months of treatment and 6 months of post-vaccination follow-up without Bactek®).

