### **9.3. Procedures for Recording and Reporting Adverse Events and Intercurrent Diseases, and for Submitting their Reports**

All events meeting the definition of an adverse event should be collected and recorded between the start of the first trial-related activity (after the subject's signature of the informed consent) and the end of the post-treatment follow-up period required by the protocol. Subjects will be questioned whether they noticed any adverse event during each visit to the site. All adverse events, whether observed by the investigator or reported by a subject, should be recorded in the corresponding section of the case report form and evaluated by the investigator.

The minimum information to be specified shall be the description, severity, duration, temporal sequence, and method of detection of the adverse event. The treatment administered to manage the event must also be specified.

The investigator shall immediately report all serious adverse events and/or suspected unexpected serious adverse events (SUSARs), regardless of their relation to the investigational medicinal product, by telephone ( [REDACTED] ) or fax ( [REDACTED] ), to the staff of Inmunotek's Medical Department (always within the first 24 hours of their onset). The initial and follow-up reports shall identify the trial subjects by a unique identification code assigned to each one of them.

[name]  
Traductor-Intérprete Jurado de INGLÉS  
Nº 9971

The regulations in force will be followed when issuing the safety information notification to the Health Authorities, the Research Ethics Committees, and the investigators.

If a suspected unexpected serious adverse reaction occurs within the context of a double-blind clinical trial, the treatment code of the particular subject must be disclosed for reporting purposes. Whenever possible, blinding should be maintained for the investigator and the persons responsible for the analysis and interpretation of the results, as well as for drafting the study conclusions.

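### SAP 7.5 compares adverse events with no on-treatment window or split by period, although about one third of planned adverse event observation time is off product

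*SAP*

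**What the plan says.** Collection. Protocol 9.3 has adverse events recorded "between the start of the first trial-related activity (after the subject's signature of the informed consent) and the end of the post-treatment follow-up period". Consent is taken at the baseline visit, which Protocol 5.2.1 places 1-4 weeks before treatment starts. The trial has a "12-month treatment period and a 6-month post-immunization follow-up period", and Protocol 7.1.4 describes the same split as "12 months of treatment and 6 months of post-vaccination follow-up without Bactek".

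Outcome. SAP 6.1.3 states the safety outcome as "Overall rate, severity, and relationship of any adverse event per administration and patient".

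Analysis. SAP 7.5 says "AEs will be summarised by System Organ Class and Preferred Term displaying number of subjects, number and percentage of subjects having the event", together with the number of events. It adds breakdowns by severity, relationship, outcome and seriousness. Qualitative safety variables are compared by chi-square, and quantitative ones by t test or a non-parametric test. Protocol 9.2 plans a similar summary by treatment group. Neither section defines treatment-emergent events or separates events before, during and after dosing. SAP 7.1 mentions descriptive safety statistics by dose, schedule and time where appropriate, but fixes no window.

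Recording window. Protocol 9.3 runs from consent to the end of follow-up. Table 1 in both documents (Protocol 5.2.1, SAP 4.1) ticks adverse event recording at visits 1-6, with no tick at baseline. Protocol 8.2 limits recording to visits 1-4, which is months 0-12.

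**The concern.** If SAP 7.5 is followed as written, the between-arm comparison takes in all recorded events whenever they began. Events from before the first dose count towards an arm, and six product-free months add background events to both arms. An excess confined to the dosing period is then measured against a larger common background, so its ratio and the power to detect it both fall. For a safety objective, a shift towards no difference is the unsafe direction.

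Two related gaps sit beside this. The stated outcome includes a rate per administration, but SAP 7.5 plans only subjects, percentages and event counts. An undivided count could not supply that rate, because it includes events from months with no administrations. And because the recording window differs between sections, the safety denominator is not fixed in advance.

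**Working it through.** **Inputs.** Dosing 12 months and follow-up without product 6 months (Protocol, Duration of the Trial and 7.1.4). Pre-dose time 1-4 weeks (Protocol 5.2.1), which at 12/52 month per week is 0.23-0.92 months. Dropout 20-25% (Protocol 10.2). No follow-up after voluntary dropout (Protocol 6.3.4). Planned size 90 per arm (Protocol 10.2). The documents give no adverse event rates, so every rate below is an assumption.

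**The plan's own figure.** 12 + 6 = 18 months per subject, as stated.

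**Off-product share, full completion** = (6 + pre-dose) / (18 + pre-dose):
- from consent, 1 week pre-dose: 6.23 / 18.23 = 34.2%
- from consent, 4 weeks pre-dose: 6.92 / 18.92 = 36.6%
- from first dose to month 18 (visits 1-6): 6 / 18 = 33.3%
- visits 1-4 only: about 0%

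The pre-dose period alone is 0.23 / 18.23 = 1.3% to 0.92 / 18.92 = 4.9%.

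**With dropout.** Let d be the dropout proportion, m the mean stopping month and r the pre-dose months, and assume no observation after stopping. Share = [6(1 - d) + r] / [18(1 - d) + d·m + r]. With m assumed between 3 and 9:
- lowest (d = 0.25, m = 9, r = 0.23): 4.73 / 15.98 = 29.6%
- highest (d = 0.20, m = 3, r = 0.92): 5.72 / 15.92 = 35.9%

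**Event-rate ratio.** Assume a constant background rate, an excess only while dosing and no carry-over. Let off be the off-product months (6.23 to 6.92). Pooled ratio = (12·RR + off) / (12 + off):

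| True on-dose ratio | off = 6.23 | off = 6.92 |
|---|---|---|
| 1.5 | 24.23 / 18.23 = 1.33 | 24.92 / 18.92 = 1.32 |
| 2.0 | 30.23 / 18.23 = 1.66 | 30.92 / 18.92 = 1.63 |
| 3.0 | 42.23 / 18.23 = 2.32 | 42.92 / 18.92 = 2.27 |

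**Subjects with an event**, which is the percentage that SAP 7.5 tabulates. Assume exponential risks, a rate ratio of 2, 2.5 weeks pre-dose (off = 6.58 months) and 90 per arm:
- 12-month placebo risk 10%: on-dose 10.0% v 19.0%, power 40%; whole period 15.0% v 23.5%, power 30%.
- 12-month placebo risk 5%: on-dose 5.0% v 9.75%, difference 4.75 points, power 23%; whole period 7.6% v 12.3%, difference 4.6 points, power 18%.

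The ratio and the power fall in both cases. The risk difference hardly moves for the rarer event.

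**The case against.** The strongest reply is that pooling is not an instruction in the plan. The SAP 7.5 sentence that covers every adverse event of the trial governs MedDRA coding only, so pooling is inferred from the absence of any split. That reading of the sentence is right. Even so, a section that sets out the safety tables and tests and names no window leaves the whole recorded period as the default.

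The plan also has partial mitigations. SAP 7.1 allows safety descriptions by time, SAP 7.5 tabulates relationship, and Protocol 9.3 records each event's temporal sequence. But SAP 7.1 is discretionary and descriptive and does not govern the tests. The relationship scale in Protocol 9.1 offers only probable, possible and unlikely, so even a pre-dose event would be graded against the product. By contrast, SAP 7.4 pre-specifies time points for exacerbations and an exposure adjustment for the Poisson model; safety has neither. The requirement of at least one dose in SAP 5.1.1 selects subjects, not events.

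A reader might infer that more than a third of the observation time is necessarily off product. That needs the pre-dose weeks to be counted and nearly all subjects to complete. The share is exactly one third from first dose, can fall to about 30% with dropout, and is near zero on the Protocol 8.2 wording.

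A reader might also infer that every product effect is diluted. It is not. An event with no background rate is unaffected, and local reactions at the administration site may come close to that. An effect that persists after dosing is not diluted in this way, and risk differences for rare events barely change. Finally, SAP 7.5 plans no event-rate ratio, and power is low under either window in the rarer-event illustrations, so the window is not the main limit on detection there.

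**Conclusion.** The concern holds for a defined class of effects. SAP 7.5 compares adverse events without an on-treatment window or period split, and on the planned schedule about one third of the observation time is off product. For effects confined to dosing that have a background rate, this reduces the contrast: an assumed event-rate ratio of 2.0 appears as about 1.63-1.66, and power in the 10% illustration falls from 40% to 30%. These sizes rest on assumed constant rates, no carry-over and the Protocol 9.3 window. Two findings need no such assumptions: the stated per-administration rate has no planned analysis, and the recording windows in Protocol 9.3, Protocol 8.2 and the two visit tables disagree. No efficacy conclusion is affected. The change should be made because it is cheap and gives a clearer safety comparison.

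**What to change.** 1. Reconcile the recording window across Protocol 5.2.1 (Table 1), 8.2 and 9.3 and SAP 4.1 (Table 1).
2. In SAP 7.5, make the main between-arm tables and tests on-treatment: onset from first dose to last dose plus a stated, justified lag. A cut at the last dose with no lag would drop late-onset events from the main test.
3. List pre-dose events. Tabulate and compare events from the end of that window to month 18 separately, so that delayed effects are seen.
4. Keep the whole-trial table as a supplement.
5. Define the per-administration rate as on-treatment events divided by doses taken, using the log sheets and returned volumes (Protocol 7.3).

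The cost is SAP wording and two more tables. The timing and dosing records needed are already collected.
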